7.2 Bayesian Analysis of Primary Outcome

The primary outcome (time to successful liberation, in ICU from mechanical ventilation) will be analyzed using accelerated failure time (AFT) models. These differ from the proportional hazards models that will be used in the primary frequentist analysis (section 5.6.1) because they require distributional assumptions for the hazards. AFT models are better suited to this context because Bayesian methods assume that all parameters have a distribution. These models will estimate time ratios, which can be interpreted as the multiplicative effect of a covariate on survival time.

As specified in the primary frequentist analysis, each transition in Figure 3 will be modelled. To maximize model flexibility, each transition will be fit to a separate AFT distribution [34]. For each transition, we will select the best model among exponential and Weibull AFT families. The model with the lowest AIC will then be modeled in INLA [35, 36].

Semi-Markov modelling will be implemented, based on clinical knowledge that the probability of transitioning would depend on the time spent in each state. For these models, time will reset to 0 when patients enter each new state.

7.2.1 Informative Prior Treatment Distribution for the Transition Between Invasive Ventilation to Liberated, In ICU

We will use an informative prior for the treatment effect on the transition between invasive ventilation to liberation, in ICU. To determine the prior, we assumed that the number of ventilator-free days in the baseline dataset would roughly correspond to the time that patients were freed from ventilation. Patients with 28 ventilator-free days were considered freed on day 0. These patients were assigned a time of 0.001, as only non-zero times could be included in AFT models. For patients with 1 to 27 ventilator-free days, the difference between 28 days and the number of ventilator-free days was considered the time to being freed from ventilation. Patients who died or started off-ventilator were excluded.

Each AFT family in the *survival* package was fit to the dataset [37]. The fitted estimates were used to generate 50000 observations from these distributions. Exponential and Weibull distributions were selected, with time ratios between the true and simulated datasets between 1 and 1.002. The AIC values, indicating the fit of these distributions to the baseline data, are presented below. The treatment effect was estimated by simulating data with incrementally decreasing location parameters within the location-scale parameterizations of the distributions. The coefficient value that generated a difference in means equal to the treatment effect in the meta-analysis (1.53 days) is reported in the table below. Standard deviations were derived by the same method with differences in means equal to estimates of the 95% confidence interval (0.83 or 2.24 days). As a conservative estimate, the standard deviation was calculated from the larger tail of the confidence interval, although estimates from either tail remained within 0.03 of each other. The MCID values were also estimated as log-time ratios using the method described above.

We will select the best fitting family, based on AIC, between exponential and Weibull distributions to model this transition with an informative prior. If there is a family that fits substantially better than exponential or Weibull, we will model this transition with a minimally informative prior for treatment in INLA.

Family	μ	σ_{100}	σ_{50}	σ_{10}	MCID	AIC
Exponential	-0.26	0.074	0.10	0.23	-0.16	10434.87
Weibull	-0.15	0.051	0.73	0.16	-0.098	8625.836

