6.6 Sensitivity Analyses

There are 2 planned sensitivity analyses based on:

- 1. Defining "successful extubation" as "48 hours without reintubation"
- 2. Assigning a value of 0 ventilator-free days to any participant who dies at any time during the study period.

7 Bayesian Analyses

The Bayesian analyses will be performed by [name], under the supervision of Drs. [name] and [name]. The goal of this analysis is to incorporate prior evidence into the analysis of the PROMIZING study. We will analyze the outcomes: time to liberation (in ICU) from mechanical ventilation and ventilator-free days. The analyses will be performed adjusted by the covariates of interest (section 3). Posterior mean, median, and 95% highest density credible intervals will be reported for all model parameters. The probability that the treatment reduces time on ventilation by the minimal clinically important difference (MCID) of 1 day will also be reported.

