7.1 Informative Prior Treatment Distributions

Our analyses will incorporate prior information from a pragmatic meta-analysis [31]. Saunders et al. reported that compared to PSV, PAV+ reduced duration on ventilation by 1.53 days (95% confidence interval: 0.83 to 2.24). The meta-analysis estimate will be weighted to 100%, 50%, and 10% to calculate prior distributions,

according to the approach in Goligher et al. [32]. Ventilator-free day data from the iCORE dataset were transformed to determine the priors for treatment effects specific to each outcome [33]. The iCORE dataset reports the number of days a patient is off ventilator within 28 days, in patients who have received PSV.

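### SAP 7.2.1: the exponential and Weibull prior rows imply control means of about 6.7 and 10.7–11.0 days for one registry dataset, so the two rows do not encode the same 1.53-day effect or the same 1-day MCID

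*SAP*

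**What the plan says.** SAP 7.1 takes its prior evidence from a meta-analysis in which "PAV+ reduced duration on ventilation by 1.53 days (95% confidence interval: 0.83 to 2.24", weighted to 100%, 50% and 10%.

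SAP 7.2.1 turns this into a prior for the transition from invasive ventilation to liberation. Registry patients with 28 ventilator-free days count as freed on day 0, and "These patients were assigned a time of 0.001, as only non-zero times could be included in AFT models". A patient whose count lies between 1 and 27 gets a time of 28 minus that count. Exponential and Weibull models are fitted, 50,000 observations are simulated from each, and the location parameter is lowered step by step. The prior centre is "The coefficient value that generated a difference in means equal to the treatment effect in the meta-analysis (1.53 days", and "The MCID values were also estimated as log-time ratios using the method described above".

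The exponential row of the table reads "Exponential -0.26 0.074 0.10 0.23 -0.16 10434.87" (centre, three SDs, MCID, AIC). The Weibull row gives −0.15, 0.051, 0.73, 0.16, −0.098 and 8625.836.

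The family for this transition is chosen by AIC. SAP 7 commits to reporting this quantity: "The probability that the treatment reduces time on ventilation by the minimal clinically important difference (MCID) of 1 day".

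**The concern.** Both rows are meant to express the same two quantities, 1.53 days and 1 day, on data from the same patients. The Weibull figures are only about 60% of the exponential ones. If the gap comes from how the models were fitted, then the effect encoded in the prior and the threshold called 1 day both depend on which family AIC selects, although the evidence has not changed. The probability of a reduction of at least 1 day would then be measured against a threshold that is not 1 day.

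**Working it through.** **1. Control mean implied by each row.** In an AFT model, a shift b in the location parameter multiplies the mean by exp(b). Hence control mean = days / (1 − exp(b)). Ranges allow for rounding of the printed coefficient.

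| Row | Calculation | Control mean, days (range) |
|---|---|---|
| Exponential, centre | 1.53/(1 − e^−0.26) | 6.68 (6.57–6.80) |
| Exponential, MCID | 1/(1 − e^−0.16) | 6.76 (6.57–6.96) |
| Weibull, centre | 1.53/(1 − e^−0.15) | 10.98 (10.66–11.34) |
| Weibull, MCID | 1/(1 − e^−0.098) | 10.71 (10.66–10.76) |

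Within each row the centre and MCID agree, which confirms this reading of the method. Between rows the means differ by about 4 days. Simulation noise is too small to explain this: the SD of a difference between two 50,000-draw means is about 0.18 day for a Weibull of this shape.

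**2. What the Weibull row means on a 6.7-day mean.**
- Centre: 6.7 × (1 − e^−0.15) = 0.93 day, not 1.53.
- MCID: 6.7 × (1 − e^−0.098) = 0.63 day, not 1.
- Closed form for 6.7 days, either family: log(1 − 1.53/6.7) = −0.259 and log(1 − 1/6.7) = −0.162.

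**3. Likely cause.** Without censoring, the exponential fit reproduces the sample mean. The Weibull fit need not, and near-zero values pull its shape down and lengthen its tail. The exponential AIC implies (10434.87/2 − 1)/(1 + ln 6.68) ≈ 1,799 events. The share of same-day liberations is not stated, so it was solved for as the share at 0.001 day that yields the printed Weibull AIC. Assumptions: several shapes for days 1–27, and 0 to 10% censored at day 28.
- At 0.001 day: share 14–23%, Weibull shape about 0.45–0.49, Weibull mean 9.8–11.1 days.
- Same data with 0.5 day: Weibull mean 6.7–7.1 days. In the runs where AIC was tracked (0 to 5% censored), the Weibull AIC was about 10,340–10,440 against 10,434.87 for the exponential. The printed advantage of 10434.87 − 8625.836 = 1,809 nearly disappears.

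**4. Effect on the reported probability (illustration).** Assume trial means of 6.7 and 7.7 days: log ratio ln(6.7/7.7) = −0.139. With 456 events (the sample-size table) and shape near 1, SE = 2/√456 = 0.094. Combine this with each printed prior by normal updating and take the probability below that row's own MCID. The Weibull 50% SD is read as 0.072 (step 5).

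| Prior weight | Weibull row | Exponential row | Gap |
|---|---|---|---|
| 100% | 0.866 | 0.822 | 0.044 |
| 50% | 0.800 | 0.699 | 0.101 |
| 10% | 0.706 | 0.483 | 0.223 |

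A fixed log ratio would not be 1 day in the trial under either row. At a 7.7-day control mean, −0.098 is 0.72 day and −0.16 is 1.14 days.

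**5. SDs.** The SAP uses the larger tail of the interval, so SD = [log(1 − 1.53/mean) − log(1 − 2.24/mean)]/1.96.
- Exponential, mean 6.68: (−0.260 + 0.408)/1.96 = 0.076, close to the printed 0.074.
- Weibull, mean 10.98: (−0.150 + 0.228)/1.96 = 0.040 (0.038–0.041 over the rounding range), against 0.051 printed.
- Weibull at 50% weight: 0.051 × √2 = 0.072, against 0.73 printed. The 10% value agrees (0.051 × √10 = 0.161, printed 0.16).

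**The case against.** Each row is correct for its own fitted distribution, and the SAP says the mapping from ventilator-free days to time holds only roughly. That explains how two different numbers arose. It does not make them the same 1.53 days or the same 1 day.

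A reader might infer that the documents prove the 0.001-day rule to be the cause. They do not. The SAP gives no day-0 share, sample size, registry mean, fitted shape or account of censoring. Only part of the assumed range matches the printed row: a Weibull mean of 9.8 days would give −0.170 and −0.108. For the same reason 6.7 days is back-calculated, not a documented registry mean.

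A reader might also take a flat-prior comparison as the size of the problem: 0.67 against the Weibull threshold and 0.41 against the exponential one in the same illustration. The plan does not use a flat prior. A flat comparison ignores that the Weibull centre is also closer to no effect, which offsets part of the easier threshold. It also treats the exponential threshold as correct; at a 7.7-day control mean 1 day is log(1 − 1/7.7) = −0.139, and the flat-prior answer is 0.50.

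Finally, the primary analysis is the frequentist multistate Cox model (SAP 6.1.1), and the Bayesian report also includes posterior summaries and credible intervals. That limits the consequence. Still, SAP 1.3.2 says both methods address the primary and secondary questions.

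**Conclusion.** The inconsistency between the rows holds and rests only on the printed table: about 6.7 days against 10.7–11.0 days for one dataset. The 0.001-day rule is the best-supported cause but remains an inference from assumed registry shapes and censoring. If 6.7 days is the right mean, the Weibull centre understates the prior effect (0.93 day instead of 1.53) and the MCID threshold is too easy (0.63 day instead of 1).

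The net effect on the reported probability is modest at full prior weight and larger at 50% and 10%. The illustrated gaps depend on the assumed trial result and on an SE for shape near 1. The issue is confined to the Bayesian analysis of the liberation transition. It does not touch the frequentist primary analysis, and the documents do not supply the correct replacement values.

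**What to change.** Before unblinding:

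1. Treat same-day liberations as interval-censored between 0 and 1 day, or use a half-day value with a sensitivity analysis on that constant. Refit both families.
2. Report the registry mean, the day-0 share and the fitted shape.
3. Derive centre, SDs and MCID for both families in closed form, log(1 − days/mean), from one stated control mean. Replace the Weibull row with the refitted values, and recheck its SDs (0.051 and 0.73).
4. Compute the probability of a reduction of at least 1 day from the posterior difference in days in the trial, not from a fixed log time ratio.

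The cost is one refit of the registry data and a revised table and paragraph in SAP 7.2.1. No trial data are needed.

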12.2 Statistical Methods Analysis

Analysis will follow the intention-to-treat principle. Baseline data will be analyzed descriptively (e.g. mean and standard deviation, median and interquartile range, counts and percentages as appropriate). Time to extubation will be summarized by cumulative incidence curves with death treated as a competing risk and compared between groups with the Gray test. The treatment effect will be expressed as a hazard ratio with 95% confidence interval from a multistate generalization of the Cox model. Additionally, a cause-specific Cox model where death is treated as a censoring event will be fit for comparison. Patients with missing outcome data will be censored at last contact. The secondary outcomes of ventilator-free days will be compared between the groups by means of a Wilcoxon test. The treatment effect will be expressed as the difference in median ventilator free days along with a 95% confidence interval obtained by bootstrap methods. The time-to-event outcomes ICU discharge and hospital discharge present the same special challenge as the primary outcome because death is a competing risk. Furthermore, "survivor-only" analyses are an improper subgroup which further complicates interpretation. To mitigate these problems, cumulative incidence curves will be constructed that provide estimates of the outcome of interest, accounting for death. Cause-specific treatment effects will be given as hazard ratios with 95% confidence intervals from Cox models. Time-to-death will be analyzed using standard methods for survival data (Kaplan-Meier curve, log-rank test) and the treatment effect will be expressed as a hazard ratio with 95% confidence interval. Four of the secondary outcomes describe weaning difficulties in various ways. These also suffer from the competing risk of death and other improper subgroup issues. These outcomes will be looked at primarily from a descriptive perspective. The outcome, "requiring A/C" will be compared by a chi-square test (or Fisher's Exact Test) and treatment difference will be expressed as an odds ratio with 95% confidence interval.

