6.2 Secondary Outcomes

The outcomes related to weaning progress and difficulties (listed below) also suffer from the competing risk of death and other improper subgroup issues. and will be looked at primarily descriptively.

- Time to death: will be analyzed using standard methods for survival data namely Kaplan-Meier curves and log-rank test. Treatment effects will be reported as hazard-ratios with 95% confidence intervals.
- Time from randomization to live ICU discharge (up to day 90) and time from randomization to live hospital discharge (up to day 90): Those two outcomes both have death as a competing risk. Cumulative incidence curves will be constructed to provide estimates of live ICU discharge and live hospital discharge that account for death. Cause-specific treatment effects on live ICU discharge and live hospital discharge will be reported as hazard ratios with 95% confidence intervals from Cox proportional hazard models.
- Time from randomization to first SBT, first successful SBT, and first extubation: These will be looked at primarily descriptively using cumulative incidence curves with death as a competing risk and compared across groups using the Gray's test.

• Ventilator-free days:

Ventilator-free days will be compared across groups using a Wilcoxon test. The treatment effect will be expressed as the difference in median ventilator-free days and its 95% confidence interval will be estimated using bootstrap methods. As per the calculation above, subjects might have 0 ventilator-free days because either they died before being liberated or they survived but remained ventilated. We

will model this using a number of approaches. For the primary analysis, we will assign the value -1 ventilator free days to subjects who died prior to liberation.

The following secondary analyses are also planned to help understand any observed treatment effect.

- Assigning the value of zero ventilator-free days to patients who died prior to being liberated from ventilation and performing a Wilcoxon test
- Poisson regression of the number of days on ventilator with the logarithm of the number of days observed as an offset
- Marginal structural model where first the probability of surviving will be modeled and then the
 weighted analysis of the survivors will be carried out using the inverse of the survival probability
 as the weight
- Invasively ventilated with tracheostomy and invasively ventilated with ETT

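### The registry fit behind the liberation prior excludes deaths, which the trial's liberation analysis censors; this shortens the fitted control time and makes the log time ratios for the prior centre and the 1-day MCID too large

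*SAP*

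**What the plan says.** SAP 7.1 takes a meta-analytic reduction of 1.53 days (95% CI 0.83 to 2.24) as the prior effect and uses a registry for control times: "The iCORE dataset reports the number of days a patient is off ventilator within 28 days, in patients who have received PSV".

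SAP 7.2.1 converts ventilator-free days into times to liberation:

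- 28 ventilator-free days: treated as freed on day 0. "These patients were assigned a time of 0.001, as only non-zero times could be included in AFT models".
- 1 to 27 ventilator-free days: "For patients with 1 to 27 ventilator-free days, the difference between 28 days and the number of ventilator-free days was considered the time" to liberation.
- Exclusions: "Patients who died or started off-ventilator were excluded".

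It gives no rule for patients alive but still ventilated at day 28. Yet SAP 6.2, writing of trial patients, recognises such a group: "subjects might have 0 ventilator-free days because either they died before being liberated or they survived but remained ventilated".

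The prior coefficient is the location shift that makes the difference in fitted means equal 1.53 days, and the MCID coefficient is found in the same way for 1 day. The printed results are -0.26 and -0.16 (exponential, AIC 10434.87) and -0.15 and -0.098 (Weibull, AIC 8625.836). The family is to be chosen by AIC.

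Elsewhere death censors liberation: in the sample-size calculation (Protocol 12.1, SAP 2.3) and in the cause-specific Cox model (SAP 6.1.2). SAP 7.3 keeps registry deaths when it builds the ventilator-free-day prior.

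**The concern.** The prior is for the transition from invasive ventilation to liberation. In a model of that transition, a patient who dies on the ventilator is at risk until death and is then censored. A patient never liberated is at risk until follow-up ends. Both add time without an event. A calibration fit that leaves them out sees only patients who were liberated, and so estimates too short a control time.

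The conversion from days to a log time ratio depends on that control time. A saving of 1.53 days is a larger proportion of a short mean than of a long one. Two outputs of the Bayesian primary-outcome analysis are affected, in opposite directions. Too large a prior centre pulls the posterior towards PAV+. Too large an MCID coefficient means that the reported probability of saving 1 day is computed for a larger saving.

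**Working it through.** **Formula.** In an accelerated failure time model a location shift b multiplies the mean by exp(b). If M is the control mean and d the days saved, b = ln(1 - d/M). As M grows, b shrinks towards zero.

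**Reproducing the printed rows.** M is not stated, so it is back-solved from the printed centre.

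- Exponential: M = 1.53 / (1 - exp(-0.26)) = 6.68 days. Then MCID = ln(1 - 1/6.68) = -0.162 (printed -0.16). The SD from the larger tail is [ln(1 - 1.53/6.68) - ln(1 - 2.24/6.68)] / 1.96 = 0.076 (printed 0.074; M = 6.76, back-solved from the MCID, gives 0.074). The row reproduces.
- Weibull: M = 1.53 / (1 - exp(-0.15)) = 10.98 days from the centre, and 1 / (1 - exp(-0.098)) = 10.71 days from the MCID. These two entries agree within rounding.

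**Restoring the deaths, exponential row.** The censored maximum-likelihood mean is total time divided by liberations. With 23.1% deaths (SAP 7.3) at mean time t, M = (0.769 × 6.68 + 0.231 × t) / 0.769. Two inputs are assumptions: t is not in the documents, and all the deaths are taken to precede liberation.

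| Assumed t (days) | M (days) | Centre | MCID | Days that -0.16 represents, M × (1 - exp(-0.16)) |
|---|---|---|---|---|
| 3 | 7.58 | -0.225 | -0.141 | 1.12 |
| 7 | 8.78 | -0.191 | -0.121 | 1.30 |
| 10 | 9.68 | -0.172 | -0.109 | 1.43 |
| 14 | 10.89 | -0.151 | -0.096 | 1.61 |

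The SD at 100% weight also changes, to between 0.064 (t = 3) and 0.040 (t = 14), so the centre and SDs must be recomputed together.

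**If unliberated survivors were also left out.** Suppose 5% of survivors were still ventilated and are now censored at day 28. That share is a further assumption. M becomes 9.1 to 12.6 days, the centre -0.184 to -0.130 and the MCID -0.116 to -0.083 over the same range of t.

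**Weibull row.** The registry data are not available, so only illustrative data sets could be built, constructed to give an exponential mean near 6.7 days. In each of those refitted, censoring deaths lengthened the Weibull mean and shrank both coefficients. In those that started from a centre of about -0.14 to -0.16, it moved to between -0.11 and -0.03. These sizes depend on the reconstruction and on the fitted tail beyond day 28, so only the direction is usable.

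**Comparison with the trial's planning figures.** Under the exponential assumption of Protocol 12.1, PSV medians of 7.40 to 7.70 days give means of 7.40/ln 2 = 10.68 to 7.70/ln 2 = 11.11 days. At those means the centre would be -0.155 to -0.148 and the MCID -0.098 to -0.094. The printed Weibull values fit this; the printed exponential values do not. At the pooled median of 6.8 days (mean 9.81) the values would be -0.170 and -0.108, slightly larger than the Weibull row.

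**The case against.** The strongest objection is that the exponential row may never be used. In the registry its AIC is about 1,800 higher than the Weibull's, and the Weibull row implies a control mean of about 11 days, close to the planning means. A reader might infer from the exclusion that the prior finally used is too favourable to PAV+ by a known percentage. The documents do not support that. Two things limit the objection. The family is still to be selected, so the exponential row remains possible. The agreement may also be partly accidental: the 0.001-day times push the Weibull shape below 1 (about 0.4 to 0.5 in the reconstructions), which stretches its mean and can offset the exclusions.

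A reader might also infer that survivors with no ventilator-free days were dropped. The SAP does not say so. They are not among the named exclusions, and the survival software used can censor them at day 28. What stands is that no rule is stated.

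The population behind the 1.53 days is not stated either. If it is survivors only, excluding deaths is partly consistent with it. If it is observed duration in all patients, the relevant mean could be 0.769 × 6.68 + 0.231 × (6 to 10) = 6.5 to 7.4 days for deaths at an assumed 6 to 10 days, giving a centre of -0.27 to -0.23, close to the printed figure. This limits what can be said about the size for the centre. It does not rescue the MCID, because Protocol 12.1 defines the 1 day for time to successful liberation, where the trial censors death.

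The 23.1% is a mortality rate, not a count of deaths before liberation. Some of those patients may have been liberated first, which would reduce the correction.

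Finally, Protocol 12.2 says that survivor-only "analyses are an improper subgroup which further complicates interpretation". It is tempting to read this as the plan condemning its own registry fit. The warning concerns comparisons between randomized groups; the registry fit is a calibration in one group, so the sentence is only loosely relevant.

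**Conclusion.** The concern holds in a limited form. Excluding registry deaths is stated, is inconsistent with how the trial treats death for this event, and biases the fitted control mean downwards. For the exponential row, with deaths at an assumed mean of 3 to 14 days and all before liberation, the printed centre is about 15% to 70% too large in magnitude (0.26/0.225 to 0.26/0.151), provided that the 1.53 days applies on the death-censored scale. The printed MCID then stands for about 1.1 to 1.6 days instead of 1.

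For the Weibull row only the direction is supported, and that only by illustration. The documents do not show that its printed values are wrong for this trial. The consequence is confined to the Bayesian time-to-liberation analysis. The primary frequentist multistate Cox analysis uses no prior, and the planned 50% and 10% weights widen the prior without moving its centre.

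**What to change.** - Refit the registry model with deaths before liberation censored at the day of death, and survivors not liberated censored at day 28. If death days are unavailable, bound them and print the prior at both bounds.
- State in SAP 7.2.1 how survivors with no ventilator-free days were handled.
- Report the fitted control mean and shape for each family, so that the conversion from days can be checked.
- Recompute the centre, the three SDs and the MCID from the refit. The Weibull SDs need checking in any case: 0.051 does not follow from the stated interval (0.040 to 0.041 at the implied means), and 0.73 is not 0.051 × √2 = 0.072.
- State whether the 1.53 days refers to survivors or to all patients. If survivors only, keep the current prior as a sensitivity analysis.

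The cost is one refit of an existing file and a new prior table, issued before unblinding; no trial data change. The drawback is that any bounds on death times are themselves assumptions.

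### The printed Weibull full-weight prior SD (0.051) does not agree with the centre and MCID in its own row, which imply about 0.040 to 0.041, so the prior labelled 100% carries roughly 61 to 65% of the meta-analysis information

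*SAP*

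**What the plan says.** SAP 7.1 takes the external evidence from a meta-analysis in which "PAV+ reduced duration on ventilation by 1.53 days (95% confidence interval: 0.83 to 2.24" days), and adds that "The meta-analysis estimate will be weighted to 100%, 50%, and 10% to calculate prior distributions". SAP 7.2.1 describes how days become log time ratios. Survival families were fitted to a baseline dataset, and "The fitted estimates were used to generate 50000 observations from these distributions". The treatment effect was then found by "simulating data with incrementally decreasing location parameters within the location-scale parameterizations of the distributions". For the prior centre, "The coefficient value that generated a difference in means equal to the treatment effect in the meta-analysis (1.53 days) is reported in the table below". For the spread, "Standard deviations were derived by the same method with differences in means equal to estimates of the 95% confidence interval (0.83 or 2.24 days"), with the choice of tail described as conservative: "the standard deviation was calculated from the larger tail of the confidence interval, although estimates from either tail remained within 0.03 of each other". Finally, "The MCID values were also estimated as log-time ratios using the method described above"; SAP section 7 sets the MCID at 1 day.

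The resulting table prints:

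| Family | Centre | SD, 100% | SD, 50% | SD, 10% | MCID |
|---|---|---|---|---|---|
| Exponential | -0.26 | 0.074 | 0.10 | 0.23 | -0.16 |
| Weibull | -0.15 | 0.051 | 0.73 | 0.16 | -0.098 |

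The divisor that turns a confidence limit into an SD is not given, nor are the fitted Weibull parameters or mean.

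**The concern.** Centre, SD and MCID all come from one mapping applied to different numbers of days, so each row should hang together. The Weibull row does not: its SD is too large for its centre and MCID.

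The labels 100%, 50% and 10% define the planned sensitivity set, and a reader will take the 100% prior to hold the meta-analysis at full strength. The SAP will also report the probability that treatment shortens ventilation by at least the MCID, and that probability depends on the prior SD. Under the Weibull prior alone (taken as normal, centre -0.15, threshold -0.098) it is 0.85 with SD 0.051 and 0.90 with SD 0.041.

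The fault is also easy to miss. The 50% entry of 0.73 is plainly wrong, being larger than the 10% entry. Anyone who repairs it by scaling from 0.051 will leave the less visible problem in place.

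**Working it through.** **Mapping.** In an accelerated failure time model a location shift b multiplies the mean m by exp(b). A difference in means of d days therefore needs

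b(d) = ln(1 - d/m).

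The larger-tail SD is [|b(2.24)| - |b(1.53)|] / 1.96. The 1.96 is my assumption. One unknown, m, fixes the row.

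**Exponential row, as a check on the mapping and divisor.**
- From the centre: m = 1.53/(1 - exp(-0.26)) = 6.68, so SD = (0.408 - 0.260)/1.96 = 0.0756.
- From the MCID: m = 1/(1 - exp(-0.16)) = 6.76, so SD = (0.402 - 0.256)/1.96 = 0.0744.
- A mean of 6.79 gives 0.074, with centre -0.255 and MCID -0.159, in line with the printed row.
- Weights: 0.074 x sqrt(2) = 0.105 (printed 0.10) and 0.074 x sqrt(10) = 0.234 (printed 0.23). Weighting therefore scales the prior variance by the inverse of the weight.

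**Weibull row.**
- From the centre: m = 1.53/(1 - exp(-0.15)) = 10.98. Then b(2.24) = -0.228 and SD = (0.228 - 0.150)/1.96 = 0.0398.
- From the MCID: m = 1/(1 - exp(-0.098)) = 10.71. Then b(1.53) = -0.154, b(2.24) = -0.235 and SD = 0.0411.
- The two cells agree within rounding. Over every rounding consistent with both, m lies between 10.66 and 10.76 and the SD between 0.0408 and 0.0413. Using the centre alone, the SD is 0.038 to 0.041.

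**Working backwards from 0.051.**
- It needs m = 8.99, which would make the centre -0.186 and the MCID -0.118. Neither matches the printed row.
- Equivalently, it places the limit at -0.15 - 1.96 x 0.051 = -0.25. At the row's own mean that is 2.37 to 2.43 days, not 2.24.

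**Other readings of the method.**

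| Reading | Weibull SD |
|---|---|
| Smaller tail | 0.036 to 0.038 |
| Full interval width | 0.038 to 0.039 |
| Divisor 1.645 | 0.047 to 0.049 |
| Means restricted to 28 days (solvable at shape 1.5 only) | 0.034 to 0.038 |

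None reaches 0.051.

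**Consequences.**
- Information at the 100% label: (0.0398/0.051)^2 = 0.61 to (0.041/0.051)^2 = 0.65.
- 10% entry: 0.051 x sqrt(10) = 0.161, the printed 0.16. From 0.041 it would be 0.13.
- 50% entry: 0.051 x sqrt(2) = 0.072, so 0.73 looks like a decimal slip. From 0.041 it would be 0.058.
- Prior 95% range in days, at m = 10.7 and centre -0.15: 0.52 to 2.37 with SD 0.051, and 0.72 to 2.20 with SD 0.041.

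**The case against.** The strongest reply is that the SAP describes a simulation, not a closed form. Step size and handling of random seeds are not given. If fresh samples of 50,000 were drawn at each step and the Weibull shape were about 0.4 to 0.5 (my assumption; the shape is not in the documents), Monte Carlo error in the SD would be about 0.007 to 0.011, enough to produce 0.051 by chance. The remark that the two tails lay within 0.03 fits a noisy search: in closed form they differ by about 0.004 for the Weibull and 0.010 to 0.011 for the exponential. The exponential check says little about this noise, since a Weibull with shape below 1 has much noisier sample means, and the printed centre and MCID are simulation outputs too.

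This stands as a possible explanation. It does not make 0.051 the value the method aims at; with common random numbers the simulated SD stays below 0.045 even at shape 0.3. Nor does the SAP's description of its choice as conservative account for the gap, because the larger tail is already used above.

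It does limit how firmly a replacement can be stated. The mean is inferred from rounded cells and the divisor is assumed, so 0.041 is what the printed row implies, not a confirmed correct value.

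It is also fair to say that an effective weight of 61 to 65% lies inside the planned 10 to 100% range, and that the primary analysis is the frequentist multistate Cox model (SAP 6.1.1).

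**Conclusion.** The Weibull row is internally inconsistent. Its centre and MCID imply a full-weight SD of about 0.040 to 0.041 against the printed 0.051, so the prior labelled 100% carries about 61 to 65% of the meta-analysis information and the 10% entry is correspondingly too wide. This rests on the divisor of 1.96 and on the printed centre and MCID being right. The effect is confined to the supplementary Bayesian analysis of time to liberation, and arises only if the Weibull family is selected. The baseline AIC values favour it (8625.836 against 10434.87).

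Three stronger readings are not supported:
- **That Weibull and exponential results under one label would be reported with unequal evidence.** SAP 7.2 and 7.2.1 select one family by AIC for this transition, and use a minimally informative prior if another family fits substantially better.
- **That the SD alone explains why 0.52 to 2.37 days differs from the published 0.83 to 2.24.** An SD of 0.041 gives 0.72 to 2.20, which also misses. The rest comes from the symmetric normal form and the rounded centre. The SD accounts for 0.72 becoming 0.52 and 2.20 becoming 2.37.
- **That the slip favours PAV+.** It widens a favourable prior, so it understates the external evidence.

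**What to change.** Recompute the whole Weibull row (centre, three SDs and MCID) from the actual fitted Weibull mean of the iCORE baseline data. Use b(d) = ln(1 - d/mean), or a simulation with common random numbers. State that mean and the divisor in SAP 7.2.1 and reprint the table.

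If the printed centre and MCID are right, expect SDs of about 0.041, 0.058 and 0.13. If the sponsor's code supports 0.051, the centre and MCID must be corrected instead. Do not repair the 0.73 entry by scaling from 0.051 before this is settled.

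The cost is a short calculation and one table row; no trial data are needed. If the SDs fall as expected, the prior becomes somewhat more influential.
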